### ***myCircadianClock application (“mCC app”)***

The mCC app is designed to run on both Android and iOS devices that account for more than 90% of all smartphones and uses HIPAA compliant Amazon Web Server (AWS) for server-side operations. A dedicated team of developers make periodic updates to the app and to the backend server to comply with updates released by Apple, Google, and Amazon. The server side is designed to run multiple independent studies and the app is designed for individual customization. This allows study-specific customization by the investigator and user-specific customizations by participants. For this specific study, the app will be customized for time-restricted eating during the intervention period. During TRE, subjects can set their daily eating periods and receive alerts and reminders specific to TRE protocols. Subjects will receive an automated alert 15 or 30 min prior to the end of the eating interval to finish their last meal of the day. All subjects can log their food, sleep, and activity. The study coordinator can visualize real-time data from individual participants and will receive a daily summary of data logs. For food entries, the user can annotate the food picture with food name and any other descriptor (portion size, left over etc.).

### ***Questionnaires***

Questionnaires will be completed via Google Forms using a GSuite that is HIPAA compliant (BAA agreement) or on a paper form. Patients will be asked to complete the following questionnaires before and after starting the intervention period: Beck Depression Inventory (BDI), Epworth Sleepiness Scale (ESS), General Health Questionnaire Short Form-36 (SF36), Pittsburgh Sleep Quality Index (PSQI) and Munich Chronotype Questionnaire (MCTQ). They will also complete mCC app-related surveys.

### ***Statistical analysis***

**Analyses for Specific Aim 1:** We will run three separate linear regressions with visit 5 levels of: 1) ADRB3 mRNA and 2) protein levels and 3) *ex vivo* response of adipose tissue to catecholamines as dependent variables, respectively. For each regression we will test group differences. For each regression model, baseline levels (visit 2) of the relevant outcomes will be included as covariates. Finally, in regression models we will explore the effect of adherence, caloric intake (estimated based on the photo and/or annotation entries on the mCC app), change in physical activity (measured by wrist-worn actigraphy devices), and weight loss. **Analyses for Specific Aim 2:** Analyses will be performed as for Specific Aim 1, but for the two inflammatory markers TNF $\alpha$  and IL1 $\beta$ . **Analyses for Specific Aim 3:** Analyses will be performed as in Specific Aim 1, but with plasma FFA levels as the dependent variable. **Exploratory Aim 1:** We will examine total body changes in fat distribution and fat mass during TRE again using linear regression models.

**Exploratory Aim 2:** We will examine the effects of TRE on multiple cardiometabolic biomarkers using linear regressions as described in Exploratory Aim 1. **Power calculation:** The goal sample size for enrollment is up to 120 participants. Accounting for a 15% attrition after enrollment, this will provide a sample size of 102 participants (n=51 in control, n=51 in TRE intervention). Using the independent samples t-test, this sample size (n=102) will have 80% power at the 0.05 significance level to detect an effect size of 0.7.

**Randomization** A study statistician will assist with randomization. We will also utilize the randomization module in RedCap as a mechanism of randomization. Participants will be randomized into the interventional TRE arm or the control group with 1:1 ratios. If multiple participants live in the same household, they will be randomized to the same group in order to maintain a consistent eating situation in the household. All investigators involved in data analysis and collection will be blinded to the randomization of participants. Only study coordinators, statistician, and dietitian will know which groups the participants are assigned to.

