#### Study visits and procedures

The study will consist of 4 or 5 in person visits over 14 weeks, as well as a 1-2-week pre-screening period which will provide a total study length of 15-16 weeks. After the 1-2-week pre-screening period where the study team determine preliminary eligibility through the participant's logging on the mCC app, the participant will undergo 2 weeks of screening/baseline and 12 weeks of intervention (Figure 3). Prior to the pre-screening period, the participant will be

**Figure 2.** Time-restricted eating (TRE) results in healthier adipose tissue, characterized by smaller lipid droplets in white (eWAT) and brown (BAT) adipose tissue on H&E staining. FAA: mice fed high-fat diet (HFD) ad lib. FTT: HFD with TRE. FTA: HFD with TRE followed by ad lib feeding. FAT: HFD with ad lib feeding followed by TRE. Arrowhead refers to crown-like structures (dead adipocytes). Chaix et al. 2014

**Figure 3.** Study design. Obese participants will undergo 2 weeks of screening/baseline, randomization to TRE versus standard of care, and 12 weeks of intervention. mCC, myCircadianClock smartphone app, CGM, continuous glucose monitor, TRE, time-restricted eating, DEXA, dual-energy X-ray absorptiometry.

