coagulation parameters (INR/PT and PTT), insulin, hs-CRP, TNF-alpha, IL1-beta, leptin, adiponectin, and plasma free fatty acids. Comprehensive blood work will be done to ensure that there are no other confounders such as renal dysfunction, anemia, hypo- or hyperthyroidism, which could influence results of the study (**See Table for Inclusion and Exclusion Criteria (below under Human Subjects)**). For women of child-bearing age, a urine pregnancy test will be performed and if positive will result in study exclusion. Using the mCC smartphone app, participants take a photo of all food and beverage they are about to consume, and the image is time-stamped and uploaded to a secure server. Study coordinators are able to monitor participant data to assess adherence with logging during the trial. A continuous glucose monitor (CGM) will be placed on the back of the upper arm, and participants will be given a wrist-worn actigraphy device to wear. Participants will be asked to use the mCC app to log all dietary intake for 2 weeks. Participants who meet inclusion criteria, including a baseline eating interval  $\geq$  14 hours during the screening period, will be randomized to TRE or standard of care. At visit 2, participants will present in the fasting state and abdominal fat biopsy will be performed: after anesthetizing skin of the abdomen with 1% lidocaine injection, a 16-gauge needle or aspiration cannula connected to a 20 mL syringe is used to obtain subcutaneous adipose tissue ( $\sim$ 0.6 g of tissue). A DEXA scan will be performed. Additional blood work may be obtained at this visit, approximately 18ml (4 teaspoons) will be collected. All participants meet with a dietitian to receive behavioral nutritional counseling. Participants in the TRE arm will self-select a 10-hour eating window. TRE is the only intervention, though all patients will be educated about the Mediterranean diet and will be encouraged to implement it in their daily lives. The control group will be given standard health and wellness guidelines and they will be advised to continue their habitual eating pattern spread over  $>14$ h. Their mCC app will be programmed so that they can visualize their own caloric intake spread over the wakeful hours. The intervention period will run 12 weeks. All participants will receive a phone call from a dietitian after 6 and 10 weeks of study enrollment to reinforce healthy dietary practices. At visit 3 (week 8) participants will return at mid-intervention and will undergo a blood draw, adipose tissue biopsy, and anthropometric measures. At visit 4 (week 12), participants will have a CGM and wrist-worn actigraphy device placed to wear for 2 weeks. At visit 5 (week 14: Study end), CGMs and wrist-worn actigraphy devices will be returned, final anthropometric measurements, fasting blood work, DEXA and fat biopsy will be performed. Participants that successfully completed the study may be invited to continue participating in optional follow-up visits (once at 6 months after study completion and once at the end of one year after study completion). We may ask participants to return for additional measurements, actigraphy watch use, continuous glucose monitoring, blood work, adipose tissue biopsy, and/or DEXA scan if they choose to participate in the optional follow-up.

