
RNA will be extracted from fat biopsy samples using standard DNA extraction kits (e.g. PureLink RNA mini kit (Life Technology)). *ADRB3*, *TNF*, and *IL1B* expression will be measured by isolating mRNA from adipose tissue biopsy samples and performing reverse transcription real-time PCR. *ADRB3* protein levels in adipose tissue biopsy samples will be measured by Western blot. Total gene expression in subcutaneous adipose tissue samples will be analyzed using

provided with the ICF via email. If the participant acknowledges their consent via email, they will enter the pre-screening period and be instructed on how to download the mCC app and log their food and beverage intake over 1-2 weeks. Only if the participant's eating window is deemed as qualifying, defined as an eating window of 14 hours or more, they will be eligible to proceed with the study and their visit 1. At visit 1 (day 1: Screening/Baseline) participants will provide written informed consent, and baseline anthropometric measurements and fasting blood tests will be obtained by standard venipuncture: comprehensive metabolic panel, complete blood count, thyroid stimulating hormone, hemoglobin A1c (HbA1c), lipoprotein by nuclear magnetic resonance (which includes standard lipid panel, lipoprotein particle numbers, and lipoprotein subfractions),

unbiased RNA sequencing analysis. Libraries will be prepared using total RNA (e.g. TrueSeq Stranded Total RNA) and will be sequenced by Illumina (e.g. Illumina HiSeq 2500 system). Bioinformatics personnel from [name] lab, in collaboration with the PI ([name]), will analyze RNA-seq data to quantify gene expression using standard software. For the *ex vivo* stimulation of adipose tissue with catecholamines, in [name] lab pieces of tissue will be added to media with isoproterenol, and media samples will be collected every 15 minutes for 1 hour. Supernatant will then be collected and combined with commercially available reagents which will be used to measure free glycerol and FFA production per mg of adipose tissue. Measurement of plasma biomarkers (e.g. lipids) will be performed using standard assays. All of the data collected as part of this study may be shared with [name] lab at the Salk Institute in its de-identified form for data analysis.

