## **12. INFORMED CONSENT**

See attached consent.

Informed consent will be obtained by the study coordinators or research assistants associated with this protocol. Informed consent procedures will be supervised either by the study coordinator, supervising physicians, or the principal investigator. All research personnel giving informed consent will have undergone proper training and obtained the required certificates.

The following are justifications for **partially waiving informed consent** for screening purposes:

1. It allows the timely review of PHI for patients who are visiting the UCSD clinics, which will allow a greater chance of finding eligible patients. It is imperative that we consent the right patients for the study in order to:
  - a. Reduce the probability of screen failures, and minimize the waste of resources, time and funds.
  - b. Conduct research more smoothly and efficiently, without having to unnecessarily disturb patients who do not

qualify for our study.

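### The same-arm rule for households does not require every member to be screened before the first is randomised, so a member who joins later would have a known arm before qualifying for entry

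*Combined protocol and SAP*

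**What the plan says.** Section 9, Statistical analysis (Randomization paragraph), sets the allocation ratio for participants: "Participants will be randomized into the interventional TRE arm or the control group with 1:1 ratios". It then adds the household rule: "If multiple participants live in the same household, they will be randomized to the same group in order to maintain a consistent eating situation". On who is unmasked it says: "Only study coordinators, statistician, and dietitian will know which groups the participants are assigned to".

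Section 9, Study visits and procedures, applies the eating-window criterion twice. The first time is in the pre-screening log of 1 to 2 weeks: "defined as an eating window of 14 hours or more, they will be eligible to proceed with the study and their visit 1". The second is in the 2-week screening log, where participants who meet the criteria, including a baseline interval of at least "14 hours during the screening period, will be randomized to TRE or standard of care". After randomisation, a TRE participant chooses a 10-hour window, and a control is advised to keep the usual pattern of more than 14 hours.

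Section 12 says: "Informed consent will be obtained by the study coordinators or research assistants associated with this protocol". The subsection of Section 9 on the smartphone app gives the coordinator a real-time view of each participant's log.

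The documents do not say whether cohabitants enrol together or in sequence, how many such households are expected, or how a later joiner is handled in the analysis.

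**The concern.** Two safeguards of a randomised comparison are that nobody involved in entry knows the next assignment, and that eligibility is settled before assignment. If the household rule is applied to someone who joins after a cohabitant has been randomised, both can fail for that person.

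- **Concealment.** The arm follows from the first member's arm. The candidate can learn it at home, and the coordinators, who may take consent and who see the logs, know it.
- **Eligibility.** The main behavioural entry criterion is an eating window of at least 14 hours. The later member would log it in a household where one person is either eating within 10 hours or has been advised to continue a long window. The protocol's own reason for the rule is that household members share an eating situation, so some influence on the log is plausible.
- **Baseline.** The visit 2 value, which is the covariate in the Aim 1 to 3 regressions, could also be taken after the household's eating had been influenced by the arm.

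At stake is whether these participants are comparable between arms at entry. This is separate from household clustering, which concerns the standard error. A cluster-robust error would change the stated precision but not who got in.

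**Working it through.** The plan gives no figure for household enrolment, so there is none to reproduce. The check has three parts: the order of events, a rough size, and an illustration of unequal entry.

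**1. Order of events (from Study visits and procedures)**

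- Logging before randomisation: pre-screening of 1 to 2 weeks plus screening of 2 weeks, so L = 1 + 2 = 3 to 2 + 2 = 4 weeks.
- Suppose a cohabitant starts logging s weeks after the first member, with the same L. The first member is randomised at week L, and the second logs from week s to week s + L. The part of the second log that falls after the first randomisation is (s + L) − L = s weeks, up to a maximum of L.
- A stagger of 2 weeks with L = 4 puts 2/4 = 50% of the qualifying log after allocation. A stagger of 3 to 4 weeks or more puts all of it there.
- Section 4 estimates 2 years for the study, and Section 11 recruits through clinics, record searches, ResearchMatch and flyers. Staggers of this length are therefore possible, although none is described.

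**2. Rough size (assumed inputs)**

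Assume that a share p of each arm are late members and that selection makes them differ between arms by g = 0.5 SD. Then the shift in the arm contrast is p × g.

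- p = 0.05: 0.05 × 0.5 = 0.025 SD.
- p = 0.10: 0.10 × 0.5 = 0.05 SD.

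For scale, the plan expects 120 × 0.85 = 102 participants, or 51 per arm. The standard error of an unadjusted difference is √(2/51) = 0.198 SD. The larger shift is 0.05/0.198 = 0.25 of a standard error. With no true effect, the two-sided 5% error rate would become Φ(−1.96 + 0.25) + Φ(−1.96 − 0.25), about 5.7%. For 0.025 SD it is about 5.2%.

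**3. Unequal entry (assumed inputs)**

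Let there be S late candidates, half in households of each arm. Let 90% qualify in control households and a proportion q in TRE households. The rest of the 120 places are filled equally between the arms. Then c = (S/2) × 0.9 and t = (S/2) × q enter late, and each arm has i = (120 − c − t)/2 other participants.

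Worked case, S = 12 and q = 0.3:

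- c = 6 × 0.9 = 5.4, t = 6 × 0.3 = 1.8, and i = (120 − 7.2)/2 = 56.4.
- Arm sizes: TRE 58.2, control 61.8.
- Late share: TRE 1.8/58.2 = 0.031, control 5.4/61.8 = 0.087, a difference of about 0.056.
- If late members differ from the others by 0.5 SD, the imbalance is about 0.028 SD. If by 1 SD, it is about 0.056 SD.

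| S | q | TRE v control | Imbalance, 0.5 SD | Imbalance, 1 SD |
|---|---|---|---|---|
| 6 | 0.6 | 59.5 v 60.5 | 0.007 | 0.014 |
| 12 | 0.6 | 59.1 v 60.9 | 0.014 | 0.028 |
| 12 | 0.3 | 58.2 v 61.8 | 0.028 | 0.056 |
| 24 | 0.1 | 55.2 v 64.8 | 0.072 | 0.145 |

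With q = 0.9 the imbalance from unequal numbers is zero. The range of about 0.01 to 0.14 SD is a baseline imbalance before any covariate adjustment. The last row needs 24 late candidates, a ninefold difference in qualifying and, for the largest value, a 1 SD offset.

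**The case against.** Much of the case on the other side stands.

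- **The rule can be read as joint randomisation.** Saying that cohabitants will be randomised to one group can mean that they are randomised together. A reader might infer that later members are in fact admitted without randomisation and that entry does differ by arm. The documents support neither statement: staggered entry is allowed by silence, and unequal entry is a possible consequence, not a reported one.
- **A reader might infer a known direction.** Those who keep a long window despite a TRE housemate and those who join because they want TRE could pull adherence and outcome in opposite ways. No direction is established.
- **A reader might infer that the baseline of late TRE members is already treated.** The two 14-hour checks limit this, because someone who has drifted to a 10-hour pattern fails them. They do not exclude it: a person whose usual window was well above 14 hours could shorten it and still qualify. The documents do not say how far one member's window moves another's.
- **Coordinators may have little room to influence entry.** Research assistants may also take consent and are not listed among those who know assignments. The log is time-stamped and the threshold is fixed. However, the plan does not say how one window is derived from 1 to 2 weeks of entries, and the candidate can know the arm whoever takes consent.
- **Such people are probably few.** A cohabitant must also have a BMI of at least 30, no diabetes, a long eating window and none of a long list of exclusions, and must accept repeated biopsies.
- **Baseline adjustment helps in part.** The Aim 1 to 3 regressions adjust for the visit 2 value, which reduces any imbalance carried by baseline level. It does not remove unmeasured selection.

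What remains is the gap in the text. Applied as written to a late joiner, the rule gives a predetermined, known arm and an eligibility log recorded after allocation.

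**Conclusion.** The concern holds in conditional form. The plan puts cohabitants in one arm without requiring them all to be screened before the first is randomised, and without excluding those who come later. If they enrol in sequence, concealment is lost for the later member, and entry could depend on arm.

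The gap is certain; how often it would matter is unknown. The effect is zero with no late joiners. Every size given above rests on assumed numbers of late members, qualifying rates and outcome differences, because the documents supply none of these. On the rough calculation it is at most about a quarter of a standard error, and only extreme inputs take it much further. The point is worth correcting because a larger sample would not average such a bias away, the planned regressions would not fully remove it, and the correction is cheap. It is not evidence that the trial's comparison is biased.

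**What to change.** 1. In the Randomization paragraph of Section 9, state that cohabitants may enrol only if every one who is to take part has consented, completed the screening log and been confirmed eligible before the household is randomised, and that the household is then randomised as one unit.
2. In the exclusion list of Section 10, add that a person whose household member has already been randomised is not eligible.
3. If any such participants have already entered, keep them in the main Aim 1 to 3 analyses and add a sensitivity analysis that leaves them out. Removing them from the main comparison would discard enrolled participants because of an unquantified risk. Record household membership and date of randomisation so that they can be identified.

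The cost is one sentence, one exclusion line and one extra analysis if it is needed. The trial would lose a few late-joining cohabitants, and a household joining together would wait until its last member had finished screening.

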### ***Banking of samples***

De-identified blood samples (specifically, serum and plasma) obtained during this study will be biobanked at UCSD or the Salk Institute for possible further analyses, such as neuroendocrine, inflammatory, and/or cardiometabolic testing. There is no intention to do genetic testing. Samples will not be shared with researchers outside of those associated with this protocol. Samples will be biobanked indefinitely. We may extend the study and provide participants with the option to return for a follow-up assessment, including repeat anthropometric and laboratory measurements.

### ***Optional Follow-Up***

Upon completion of the study, subjects who are still adhering to TRE may be invited to continue participating in optional follow-up visits (once at 6 months and once at the end of one year) if subjects wish to maintain dietary intake limited to 10 hours per day and will continue to record dietary intake using the smartphone application. Subjects that were in the standard of care group may be invited to participate in follow-up visits as well and will continue to log using the application. All subjects may be asked for additional measurements, blood work, adipose tissue biopsy, and/or DEXA scan at these optional follow-up visits.

## **10. HUMAN SUBJECTS**

We aim to enroll up to 120 participants (accounting for a 15% attrition after enrollment, this will provide a sample size of 102 participants)  $\geq 18$  years (all genders and races/ethnicities) with obesity ( $BMI \geq 30 \text{ kg/m}^2$ ) (without T2DM) and a baseline eating duration of  $\geq 14$  hours/day. Participants will be recruited from the cardiovascular and internal medicine clinics at UCSD. In addition, we will utilize the bioinformatics report generated from EPIC to assist in recruitment. The inclusion and exclusion criteria are below (**Table**).

The main site of the interviews and clinical testing (vitals, blood draw, adipose tissue biopsy, DEXA) will be the UCSD Altman Clinical and Translational Research Institute (ACTRI). Blood will be processed at the UCSD Clinical Laboratory.

**Table.** Inclusion and exclusion criteria

Inclusion criteria:	Exclusion criteria:


• Age <math>\geq 18</math> years

• Body mass index (BMI) <math>\geq 30 \text{ kg/m}^2</math>

• Own a smartphone (Apple iOS or Android OS)

• Baseline eating period <math>\geq 14</math> hours/day

• If patients are on cardiovascular medications (HMG CoA reductase inhibitors (statins), other lipid modifying drugs (including over the counter drugs such as red yeast rice and fish oil), anti-hypertensives), no dose adjustments will be allowed during the study period

	

• Anti-diabetic medications or insulin within the last 6 months

• Manifest diabetes, defined as fasting glucose <math>\geq 126 \text{ mg/dL}</math>, HbA1c <math>\geq 6.5\%</math>, or diagnosis of diabetes

• Currently taking any medication that is meant for, or has known effect on, appetite or body weight.

• Pregnant or breast-feeding

• Caregiver for a dependent requiring frequent nocturnal care/sleep interruptions. Shift workers with variable (e.g. nocturnal) hours

• Prolonged international travel (time zone changes) during the study period

• Taking therapeutic anticoagulation which might increase risk of bleeding from fat biopsy

• History of surgical intervention for weight loss

• Currently enrolled in a weight-loss or weight-management program

• On a special or prescribed diet for other reasons (e.g. Celiac disease)

• Known inflammatory and/or rheumatologic disease

• Active tobacco abuse or illicit drug use or history of treatment for alcohol abuse

• History of bone marrow or solid organ transplant

• History of heart failure

• History of major adverse cardiovascular events (acute coronary syndrome (ACS), percutaneous coronary intervention, coronary artery bypass graft surgery, stroke/transient ischemic attack (TIA)).

• History of atrial fibrillation or atrial flutter

• History of malignancy, other than non-melanoma skin cancer, that is currently being treated, or that has not been treated with definitive therapy and considered to be in remission.

• History of hypo- or hyperthyroidism requiring dose titration of thyroid replacement medication(s) within the past 3 months (i.e. hypothyroidism on a stable dose of thyroid replacement therapy is not an exclusion)

• History of adrenal disease

• History of eating disorder

• History of cirrhosis

• History of stage 4 or 5 chronic kidney disease or requiring dialysis

• History of HIV/AIDS

• Uncontrolled psychiatric disorder (including history of hospitalization for psychiatric illness).

• History of obstructive sleep apnea (not on stable positive pressure therapy or other treatment for at least 3 months prior to enrollment)

